9.3.2 Exclusion Criteria

Subjects who meet any of the following criteria will be excluded from this study:

1. Females who are breastfeeding or pregnant at Screening or Baseline (as documented by a positive beta-human chorionic gonadotropin test. A separate baseline assessment is required if a negative screening pregnancy test was obtained more than 72 hours before the first dose of study drug. Females of child-bearing potential who:
 - within 28 days before study entry, did not use a highly effective method of contraception, which includes any of the following:
 - total abstinence (if it is their preferred and usual lifestyle)
 - an intrauterine device or intrauterine hormone-releasing system
 - an oral contraceptive (Subject must be on a stable dose of the same oral contraceptive product for at least 28 days before dosing and throughout the study and for 28 days after study drug discontinuation.)
 - have a vasectomized partner with confirmed azoospermia
 - do not agree to use a highly effective method of contraception (as described above) throughout the entire study period and for 28 days after study drug discontinuation.

For sites outside of the European Union, it is permissible that if a highly effective method of contraception is not appropriate or acceptable to the subject, then the subject must

agree to use a medically acceptable method of contraception, ie, double-barrier methods of contraception such as condom plus diaphragm or cervical/vault cap with spermicide.

NOTE: All females will be considered to be of child-bearing potential unless they are postmenopausal (amenorrheic for at least 12 consecutive months, in the appropriate age group, and without other known or suspected cause) or have been sterilized surgically (ie, bilateral tubal ligation, total hysterectomy, or bilateral oophorectomy, all with surgery at least 1 month before dosing)

2. Any condition that may be contributing to cognitive impairment above and beyond that caused by the subject's AD
3. Subjects with a history of seizures within 5 years of Screening or subjects with disturbance likely to be due to seizures within 5 years of Screening
4. History of transient ischemic attacks (TIA) or stroke within 12 months of Screening
5. Modified Hachinski Ischemia Score greater than 4 at Screening
6. Any of the following psychiatric symptoms:
 - Psychiatric diagnosis or symptoms, (eg, hallucinations, major depression, or delusions) that, in the opinion of the investigator, could interfere with study procedures
 - Has a "yes" answer to C-SSRS suicidal ideation items 4 or 5, or any suicidal behavior within 6 months before Screening, at Screening, or at the Randomization Visit, or has been hospitalized or treated for suicidal behavior in the past 5 years before Screening
7. Have any contraindications to MRI scanning, including cardiac pacemaker/defibrillator, ferromagnetic metal implants (eg, in skull and cardiac devices other than those approved as safe for use in MRI scanners) or
 - Have any evidence of other clinically significant lesions that could indicate a dementia diagnosis other than AD on brain MRI at Screening.
 - Exhibit other significant pathological findings on brain MRI at Screening, including but not limited to: an area of superficial siderosis; evidence of cerebral vasogenic edema; evidence of cerebral contusion, encephalomalacia, aneurysms, vascular malformations, or infective lesions; evidence of multiple lacunar infarcts or stroke involving a major vascular territory, severe small vessel, or white matter disease; space occupying lesions; or brain tumors (however, lesions diagnosed as meningiomas or arachnoid cysts and less than 1 cm at their greatest diameter need not be exclusionary).
8. Subjects who have a history of moderate to severe hepatic impairment (eg, Child-Pugh Class B or C). Any 2 of the following criteria at Screening would exclude the subject: INR ≥ 1.7 ; bilirubin $\geq 1.5 \times$ ULN; albumin $<$ LLN; ascites or hepatic encephalopathy. Please note that a single

significant abnormality could meet criteria for moderate impairment. (revised per Amendment 01)

9. Results of laboratory tests conducted during screening that are outside the following limits:

- Absolute lymphocyte count (ALC) below Lower Limit of Normal (LLN) or below 800 per mm³ (whichever is higher); ALC will be derived from the complete blood count (CBC) with differential representing the normal lymphocytes (with atypical lymphocytes removed and presented as a separate count if they are present) and calculated by the white blood cell count × percentage of lymphocytes. (revised per Amendment 01)
- Thyroid stimulating hormone (TSH) above normal range. Other tests of thyroid function with results outside the normal range should only be exclusionary if they are considered clinically significant by the investigator (this applies to all subjects whether or not they are taking thyroid supplements)
- Abnormally low (below LLN) serum Vitamin B12 levels (if subject is taking Vitamin B12 injections, level should be at or above the LLN)

10. Subjects at risk of increased risk of infection, specifically:

- Subjects with chronic viral hepatitis, a history of active tuberculosis disease (TB), ophthalmic shingles or ocular herpes simplex virus (HSV) infection
- Any active infection within the last 4 weeks before randomization. For such cases, the timing of randomization can be extended (up to 4 weeks) to allow the infection to resolve
- Any immunological disease which is not adequately controlled, or which requires treatment with biologic drugs during the study. History of immunoglobulin deficiency or other immunodeficiency disorders (including subjects known to be HIV positive)

11. Have received any live/live attenuated vaccine in the 3 months before randomization

12. Any chronic inflammatory disease that is not adequately controlled or that requires systemic or ocular immunosuppressive or immunomodulatory therapy.

NOTE: The following subjects do not need to be excluded:

- Subjects with seasonal or perennial allergic rhinitis, asthma, or chronic obstructive pulmonary disease where the condition is considered to be stable and adequately controlled by inhaled steroids.

- Hashimoto's thyroiditis but who are stable on thyroid replacement therapy and not on systemic immunosuppressive therapy.
- Cutaneous manifestations of immunological disease that do not require systemic immunosuppressive therapy or systemic immunomodulatory therapy (ie, topical steroid treatment is permitted)

13. Any other clinically significant abnormalities, such as:

- Physical examination, vital signs, laboratory tests or ECG at Screening or Baseline which in the opinion of the investigator require further investigation or treatment or which may interfere with study procedures or safety.
- Other medical conditions (eg, cardiac, respiratory, gastrointestinal, psychiatric, renal disease) which are not adequately and stably controlled, or which in the opinion of the investigator(s) could affect the subject's safety or interfere with the study assessments (revised per Amendment 01)
- Illiteracy, or severe visual or hearing impairment that would prevent the subject from performing psychometric tests accurately

14. A prolonged QTc interval calculated using Fridericia's formula (QTcF) interval (QTcF greater than 450 ms). If the QTcF is greater than 450 ms on the first single 12-lead ECG, 2 additional 12-lead ECGs will be performed 1 minute apart and the mean of the 3 QTcF values will be calculated.

15. Malignant neoplasms within 5 years of Screening (except for basal or squamous cell carcinoma in situ of the skin, or localized prostate cancer in male subjects with treatment cycles completed at least 6 months prior to screening). Subjects who had malignant neoplasms but who have had at least 5 years of documented uninterrupted remission before Screening need not be excluded.

16. Hypopigmentation conditions (eg, albinism and vitiligo). Hypopigmentation associated with scarring need not be exclusionary

17. Known or suspected history of drug or alcohol abuse or dependence within 2 years before Screening

18. Taking prohibited medications

19. Have participated in a clinical study involving:

- any therapeutic monoclonal antibody, protein derived from a monoclonal antibody, immunoglobulin therapy, or vaccine within 6 months before Screening for whom it cannot be documented that they were randomized only to placebo or never received study drug

- elenbecestat (E2609)
- any new chemical entity for AD with last study drug dose occurring within 6 months prior to Screening unless it can be documented that the subject received only placebo
- any other investigational medication (unless it can be documented that the subject received only placebo) or device within 8 weeks or 5 half-lives (whichever is longer) before randomization

20. Planned surgery which requires general, spinal or epidural anesthesia that would take place during the study. Planned surgery which requires only local anesthesia and which can be undertaken as day case without inpatient stay postoperatively need not result in exclusion if in the opinion of the investigator this operation does not interfere with study procedures and subject safety.

9.3.3 Removal of Subjects from Therapy or Assessment

The investigator may withdraw the subject from the study at any time for safety or administrative reasons. The subject may stop study drug or withdraw from the study at any time for any reason.

Absolute lymphocyte count from the hematology and differential panel will be monitored during the study. ALC will be derived from the CBC with differential representing the normal lymphocytes (with atypical lymphocytes removed and presented as a separate count if they are present) and calculated by the white blood cell count \times percentage of lymphocytes. (revised per Amendment 01) Should a subject develop a Grade 2 or greater lymphocytopenia (less than $800/\text{mm}^3$), this should be confirmed as soon as possible but no later than within 5 days with a repeat test of absolute lymphocyte count. If confirmed, study drug administration should be interrupted for a minimum period of 2 weeks and for a maximum period of 4 weeks. Restart of study drug may take place only when absolute lymphocyte count returns to greater than LLN. Absolute lymphocyte count will be measured 4 weeks after restart of study drug. Subsequent measurements of absolute lymphocyte counts will follow the schedule of assessments (Table 3) and any results showing a Grade 2 or greater lymphocytopenia (less than $800/\text{mm}^3$) should be handled as above. If a 2nd occurrence of Grade 2 or greater lymphocytopenia (less than $800/\text{mm}^3$), that is confirmed on repeat testing, occurs within 6 months, then the subject should be discontinued permanently from the study drug.

Subjects who develop moderate or severe hepatic impairment during the study must discontinue study drug. (revised per Amendment 01)

Subjects who discontinue study drug early must complete the ED Visit (within 7 days of the last dose of study drug) and the Follow-Up Visits (1 and 3 months after the last dose of study drug). These Follow-Up Visits will be conducted to monitor efficacy and safety parameters after early withdrawal from the study or discontinuation of study drug.

All subjects who discontinue study drug before reaching 12 months of treatment will also be asked to return to the clinic for a 12-month clinical assessment and then again at 24 months. Subjects who discontinue treatment between 12 and 24 months of treatment will be asked to return to the clinic for a 24 month clinical assessment. Subjects who discontinue early from study drug are considered “on study” as long as they continue to return for their regularly scheduled clinical assessments at 12 and 24 months as outlined above, at which efficacy and quality of life will be assessed along with concomitant medications and AEs. However, subjects who discontinue study drug early are not considered to have ‘completed’ the study as a final Subject Disposition.

The primary reason for discontinuation and all other reason(s) contributing to the subject’s discontinuation from study drug(s) should be collected on the ED from study drug electronic case report form (eCRF) page. In addition, the date of last dose of study drug(s) will be recorded on the Study Drug Dosing eCRF page. If a subject discontinues study treatment and the study at the same time, the end-of-study procedures (Final Visit) will be followed (see [Section 9.5.5](#)).

9.4 Treatment(s)

9.4.1 Treatment(s) Administered

For this study the test drug is elenbecestat (E2609) and the control drug is placebo. All study drug is to be administered orally, once daily (QD), in the morning with or without food. As shown in [Figure 1](#), there will be 2 treatment arms where the elenbecestat (E2609) arm will be administered a single dose of 50 mg per day and the control arm will be administered placebo.

Study treatment will begin on Day 1 (at the study site) following randomization and will continue for approximately 24 months. Please refer to [Table 3](#) and [Section 9.5.1.4.1](#) for specific information regarding study drug administration on days when PK sampling is to be performed.

Study drug dose will remain the same for each individual subject throughout the duration of the study. If a subject develops a concurrent illness during the treatment period, the investigator should discuss with the medical monitor on whether dosing with study drug needs to be temporarily suspended. As a general clinical guideline, dosing with study drug may be resumed after resolution or stabilization of the concurrent illness, after discussion with the medical monitor.

Rules for discontinuing study treatment for subjects due to skin rash or to severe infections are described in [Section 9.5.1.5.5](#).

9.4.2 Identity of Investigational Product(s)

Elenbecestat (E2609) will be supplied by the sponsor as tablets of 50-mg dose strength in bottles of 35 tablets each. Placebo tablets to match elenbecestat (E2609) will be of identical appearance. Each subject will receive 1 tablet of 50 mg elenbecestat (E2609) or an identical

placebo tablet, to be administered orally QD in the morning with or without food. The product release certificates for elenbecestat (E2609) and placebo will be included in the clinical study report for this protocol.

Subjects will be stratified and randomized, and drug will be dispensed, via an interactive voice and web response system (IxRS) system (see [Section 9.4.3](#)).

The sponsor will provide the study drugs packaged in a double-blind configuration. Each subject's study tablets will consist of either elenbecestat (E2609) or placebo (see [Section 9.4.2.3](#) for labeling details).

9.4.2.1 Chemical Name, Structural Formula of Elenbecestat (E2609)

- Test drug code: E2609
- Generic name: elenbecestat (pINN)
- Chemical name: International Union of Pure and Applied Chemistry
N-{3-[(4*aS*,5*R*,7*aS*)-2-Amino-5-methyl-4*a*,5-dihydro-4*H*-furo[3,4-*d*][1,3]thiazin-7*a*(7*H*)-yl]-4-fluorophenyl}-5-(difluoromethyl)pyrazine-2-carboxamide
- Molecular formula: C₁₉H₁₈F₃N₅O₂S
- Relative molecular mass: 437.44

9.4.2.2 Comparator Drug

Not applicable.

9.4.2.3 Labeling for Study Drug

Elenbecestat (E2609) will be labeled in accordance with text that is in full regulatory compliance with each participating country and is translated into the required language(s) for each of those countries. The following information may be included but is not limited to:

- Protocol number
- For clinical study use only
- Name and address of the sponsor
- Chemical name/drug identifier
- Lot number/batch number
- Storage conditions, expiration date if necessary

9.4.2.4 Storage Conditions

Study drug will be stored in accordance with the labeled storage conditions. Temperature monitoring is required at the storage location to ensure that the study drug is maintained within an established temperature range. The investigator or designee (or if regionally

required, the head of the medical institution) is responsible for ensuring that the temperature is monitored throughout the total duration of the study and that records are maintained; the temperature should be monitored continuously by using either an in-house validated data acquisition system, a mechanical recording device, such as a calibrated chart recorder, or by manual means, such that minimum and maximum thermometric values over a specific time period can be recorded and retrieved as required.

9.4.3 Method of Assigning Subjects to Treatment Groups

Subjects will be assigned to treatments based on a computer-generated randomization scheme that will be reviewed and approved by an independent statistician. The randomization scheme and identification for each subject will be included in the final clinical study report for this study. The doses and number of treatment groups to be used are described in [Section 9.4.1](#).

Stratification and randomization will be performed centrally by an IxRS. The IxRS or clinical supply vendor will generate the randomized bottle identification numbers. At enrollment (Screening), the investigator or designee will call the IxRS to register the subject information. At randomization (Visit 2), the IxRS will assign each subject a unique randomization number.

9.4.4 Selection of Doses in the Study

Selection of elenbecestat (E2609) 50 mg per day is based on the results (PD, safety, and tolerability) from the completed Phase 1 studies and interim data from the ongoing Phase 2 Study 202. Study 202 is currently evaluating the PD effects (reduction from baseline in CSF A β levels) of 5, 15, and 50 mg of elenbecestat (E2609) given daily. An interim PD analysis has been performed on the degree of CSF A β reduction achieved with elenbecestat (E2609) 5, 15, and 50 mg per day. Based on these results elenbecestat (E2609) 50 mg per day produced relatively high levels of CSF A β reduction (greater than 50%) and this, in turn, should translate into greater clinical benefit while minimizing the safety concerns. Based on these data, elenbecestat (E2609) 50 mg per day dose was selected as a viable dose for this study. Subjects will be stratified according to region (7 levels), clinical dementia staging with no more than approximately 25% of the randomized subjects diagnosed with the early stages of mild dementia due to AD, and concurrent AD medication use.

9.4.5 Selection and Timing of Dose for Each Subject

Elenbecestat (E2609) is administered orally, QD, in the morning with or without food. Study treatment will begin on Day 1 following randomization and will continue for 24 months.

9.4.6 Blinding

Elenbecestat (E2609) and placebo will be administered as tablets of identical appearance.

During the Randomization and Follow-Up Phases, subjects and all personnel involved with the conduct and interpretation of the study, including investigators, site personnel, and

sponsor staff will be blinded to the treatment codes (double-blind). Randomization data will be kept strictly confidential, filed securely by an appropriate group with the sponsor or CRO, and accessible only to authorized persons (eg, Eisai Global Safety) until the time of unblinding, per the standard operating procedure.

PK and PD data will be provided to the sponsor by the PK and PD analysis laboratories using dummy subject numbers instead of actual subject numbers. The same dummy subject number will be used for a subject's PK and PD data. These data will be used to evaluate whether the PK and PD effects seen in this study are similar to those seen in previous studies. Thereafter, unblinded PK and PD data will only be provided to the sponsor after study completion.

In the event that emergency conditions require knowledge of the study treatment given, the blind may be broken via the code breaker facility within the IxRS. Emergency procedures for revealing drug codes are given in [Section 9.5.4.5](#). If possible, before breaking the blind, the investigator should consult with the sponsor to ascertain the necessity of breaking the code. If an AE results in the investigator breaking the blind, then that AE must be reported as a SAE.

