9.5.1.4.2 PHARMACODYNAMIC, PHARMACOGENOMIC, AND OTHER BIOMARKER, ASSESSMENTS

Biomarkers

The CSF sample will be used for PD assessments including but not limited to CSF A β (1-x), A β (1-42), A β (1-40), t-tau, p-tau, and BACE1 levels and activity.

The plasma sample will be used for A β (1-x) analysis and may be used for exploratory biomarker analyses. A β (1-x) in both CSF and plasma will be measured using a modified commercially available enzyme-linked immunosorbent assay (ELISA). The prescreening and postscreening analysis of CSF A β (1-42), A β (1-40), t-tau, and p-tau will be performed using commercially available ELISAs. BACE1 levels will be measured using internally developed fluorescence resonance energy transfer and ELISA based assay(s). Substrates of BACE1 inhibition may also be explored using Western blots or other amenable methodology if clinical observations warrant and if analytes can be reliably tested in samples collected.

Blood samples will be collected for PD assessments as specified in [Table 2](#) and [Table 3](#). The blood sample collected for PD analyses at Screening should be collected at fasting or at least 2 hours after the most recent meal and PD blood samples should be taken predose at Visits 3, 4, 6, 7, 9, 11, and 13 (or ED) and, as far as is feasible, samples should be taken at the same time of day

Blood samples and CSF (if applicable) collected at Screening will be stored for determination of prior exposure to any suspected infective agents in the event that the subject develops TEAEs that warrant further investigation (eg, treatment-emergent infection). Testing may include, but not be limited to, serological tests (eg, HSV1 and 2), viral titer by quantitative polymerase chain reaction (Q-PCR), and/or human leukocyte antigen (HLA) genotyping.

For all subjects, baseline and on-study blood samples, DNA samples, and any collected CSF samples (if applicable) will be stored for up to 15 years.

See the laboratory manual (to be supplied to study sites) for a description of the collection, handling, and shipping procedures of the biomarker samples.

Pharmacogenomics

A blood sample will be obtained at Screening and will be used to determine the *ApoE* genotype of subjects enrolled in this study. The findings will be used in the statistical analysis to determine the effects on treatment response and safety.

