9.7.1 Statistical and Analytical Plans

All statistical analyses will be performed by the Sponsor or designee after the study is completed and the database is locked and released for unblinding.

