9.7.1.7.3 PHARMACODYNAMIC, PHARMACOGENOMIC, AND OTHER BIOMARKER ANALYSES

The analysis of the biomarker endpoints defined as below will be performed to compare elenbecestat (E2609) versus placebo using the appropriate prespecified statistical methods including MMRM model, analysis of covariance model (ANCOVA), etc. These analyses will be conducted without adjustment for multiplicity or sequential testing. For each endpoint, the treatment effect for elenbecestat (E2609) 50 mg per day versus placebo will be tested at a significance level of 2-sided alpha = 0.05.

- Change from baseline in amyloid PET SUVR composite at 24 months for brain amyloid levels
- Change from baseline in CSF biomarkers t-tau and p-tau at 24 months
- Change from baseline in CSF amyloid biomarkers $A\beta(1-40)$, $A\beta(1-42)$, and $A\beta(1-x)$ at 24 months
- Change from baseline in total hippocampal volume at 12 and 24 months using vMRI
- Change from baseline in the preservation of connectivity on fMRI from predefined anatomical regions connectivity maps (eg, precuneus, inferior frontal sulcus)

The relationship between exposure (in CSF, plasma) of elenbecestat (E2609) with potential biomarkers of Alzheimer's disease as deemed appropriate will be evaluated using appropriate statistical model with the continuous changes in biomarker at 24 months as response variables and exposure variables (in CSF, plasma) of elenbecestat (E2609) as independent variables.

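### Section 9.4.6 lets sponsor staff receive linked PK and PD data before study completion without excluding CSF t-tau and p-tau, so arm-level results on these endpoints could be seen before database lock

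*Protocol*

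**What the plan says.** Section 9.4.6 says that through the Randomization and Follow-Up Phases "sponsor staff will be blinded to the treatment codes (double-blind"). The same section then provides that "PK and PD data will be provided to the sponsor by the PK and PD analysis laboratories using dummy subject numbers". It adds: "The same dummy subject number will be used" for both kinds of data from one subject. The purpose is given: "These data will be used to evaluate whether the PK and PD effects seen in this study are similar" to those of previous studies. The paragraph closes by saying that, thereafter, unblinded PK and PD data come to the sponsor only once the study is complete. For randomization data the section restricts access to authorized persons. For the PK/PD files it names no recipients, analytes or dates.

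Section 9.5.1.4.1 has every active-arm PK sample assayed, but only a preset percentage of placebo samples. Section 9.5.1.4.2 says "The CSF sample will be used for PD assessments including but not limited to CSF" Abeta(1-x), Abeta(1-42), Abeta(1-40), t-tau, p-tau and BACE1. Sections 9.7.1.1.4 and 9.7.1.7.3 list "Change from baseline in CSF biomarkers t-tau and p-tau at 24 months" among the biomarker endpoints, alongside the CSF Abeta species, each tested at two-sided 0.05. Section 9.7.1 places all statistical analyses "after the study is completed and the database is locked and released for unblinding".

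**The concern.** Dummy numbering protects identity, not allocation. In a placebo-controlled trial, a file that holds drug concentrations is in effect labelled by arm. Joining PD values to it through a common number turns it into a by-arm PD data set. If those PD values include t-tau and p-tau, sponsor staff could compare two named endpoints by arm while the trial is running.

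Several sponsor decisions are still open at that stage. The futility boundary is nonbinding and sample-size re-estimation is allowed (9.7.3). The order of the secondary endpoints is to be set before lock (9.7.1.6.2), as are the per-protocol criteria (9.7.1.2). The SAP may be revised after the study starts (9.7.5). Staff who had seen arm-level tau results could not credibly be called blinded when taking those decisions, whether or not the results influenced them.

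**Working it through.** The protocol attaches no figure to this point, so the check consists of reading the sections against each other.

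1. **When.** Section 9.4.6 describes the dummy-coded transfer first. It then says that from that point on, unblinded data wait for study completion. The natural reading is that the dummy-coded files arrive before completion. This is an inference.

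2. **Does the file show the arm?** Under section 9.5.1.4.1, subjects on PK days take study drug at the clinic after the predose sample and are sampled again 1 to 6 hours later (Visits 3, 4, 6, 7, 9 and 11) or 4 to 8 hours later (Visit 13). A record with quantifiable elenbecestat is active. An assayed record without it is placebo, apart from subjects who have already stopped drug. Because the dose is taken on site, poor adherence at home should blur this little.

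3. **Does the pattern of assayed samples add to this?** All active samples but only some placebo samples are assayed for drug. The synopsis (Bioanalytical Methods) has CSF t-tau and p-tau measured in all collected samples. A dummy record with CSF results and no PK results would therefore also point to placebo.

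4. **Are the PD values tied to that label?** Yes, through the shared number: "The same dummy subject number will be used" for a subject's PK and PD data.

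5. **Do the PD values include endpoints?** Section 9.5.1.4.2 lists t-tau and p-tau as CSF PD assessments, and section 9.7.1.1.4 lists their 24-month change as endpoints. Section 9.4.6 does not say which PD analytes are sent, so they are not excluded. Their inclusion is possible, not established.

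6. **What is outside the exposure?** CDR-SB is not part of PK/PD laboratory data, and the dummy number prevents a direct link to it. Nothing shows amyloid PET, vMRI or fMRI results coming from these laboratories.

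7. **How much early information?** Post-baseline CSF is collected only at 24 months, or at an early discontinuation visit after at least 39 weeks of drug (9.1.2.1), and only in an optional substudy. Neither substudy uptake nor any transfer date is stated, so the quantity cannot be computed.

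**The case against.** The best defence is that 9.4.6 never says tau is sent. Sections 7.1 and 9.4.4 describe the PD effect in Study 202 as reduction in CSF Abeta, and the synopsis pairs plasma Abeta(1-x) with the PK draws. A comparability check could be one early transfer of PK and Abeta, with almost no post-baseline CSF in it. Sponsor staff are said to be blinded to treatment codes, and no identified subject's code is revealed. A comparability check is also not the endpoint test that section 9.7.1 reserves for after lock. The CSF endpoints are laboratory assays, outside the sequential testing of secondary endpoints and without multiplicity control. A firewall may exist in a document not shown.

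Much of this stands. It limits the point to what the text permits, and to CSF tau as the material exposure. The CSF Abeta species are endpoints too, but section 9.4.4 already reports a reduction above 50% at 50 mg, so seeing it by arm would reveal little. It does not remove the point, because the rule as written allows the access and sets no limit on analyte, recipient or time.

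Three stronger readings are tempting and not supported:

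- **The primary endpoint is unblinded.** The dummy number blocks a direct link to CDR-SB, and no effect on the primary type I error follows.
- **The early information can be sized at the futility analysis.** A reader might take 0.30 × 1330 = 399 subjects, assume 20% to 50% CSF uptake, and get about 40 to 100 per arm. From (1.96 + 0.84) × √(2/m), that would detect 0.63 to 0.40 SD with 80% power. Counting 30% of expected completers instead (0.30 × 0.70 × 1330 ≈ 279) gives about 28 to 70 per arm and 0.75 to 0.47 SD. The uptake is invented in both cases, and nothing ties a transfer to the futility date.
- **The stated purpose needs no CSF data.** CSF Abeta is the very effect measured in Study 202, so barring it outright would remove a main comparator.

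**Conclusion.** The point holds in limited form. As written, section 9.4.6 permits a pre-completion file that shows the arm and may carry CSF t-tau and p-tau, which conflicts with its own statement that sponsor staff are blinded. The harm is to the integrity of those two endpoints and to the credibility of sponsor decisions taken before lock. No power or alpha figure can be attached to it.

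The conclusion rests on two inferences: that the transfer precedes study completion, and that PD in 9.4.6 carries the meaning it has in 9.5.1.4.2. If another document already limits analytes and recipients, the remaining task is to bring 9.4.6 into line with it. This corrects a stated rule and is not a request for detail that belongs in the SAP.

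**What to change.** Amend 9.4.6, and the data-transfer plan to match, as follows:

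- Limit the pre-lock transfer to PK and Abeta: plasma Abeta(1-x), and CSF Abeta if it is needed for the comparison with Study 202.
- Send times relative to dose, not calendar dates, so that the sampling windows remain usable.
- Restrict receipt to PK/PD staff who have no role in trial conduct, SAP revision, futility or sample-size decisions.
- Hold CSF t-tau, p-tau and the exploratory neurodegeneration markers at the laboratory until database lock and unblinding.

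The cost is a few sentences. The downside is that any early look at these markers against earlier studies waits until unblinding. If CSF Abeta is sent, those Abeta endpoints remain visible by arm to the restricted group, which the restriction on recipients is meant to contain. Visits, sampling and clinical management are unaffected.
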